6.2 Exclusion Criteria

1) Medical Conditions

- a) Cohort M1, M2, and C1: Untreated or active central nervous system (CNS) or leptomeningeal metastases. Patients are eligible if metastases have been treated and patients are neurologically returned to baseline or neurologically stable (except for residual

signs or symptoms related to the CNS treatment) for at least 2 weeks prior to treatment assignment. In addition, patients must be either off corticosteroids, or on a stable dose or decreasing dose of <10 mg daily prednisone or prednisone equivalent

- b) Cohort M1, M2, and C1: Subjects with hepatocellular carcinoma (HCC)
- c) Cohort C2: Subjects with solitary bone or extramedullary plasmacytoma as the only evidence of plasma cell dyscrasia
- d) Cohort C2: Subjects with monoclonal gammopathy of undetermined significance (MGUS), smoldering multiple myeloma (SMM), amyloidosis, Waldenstrom's macroglobulinemia, or POEMS syndrome (plasma cell dyscrasia with poly neuropathy, organomegaly, endocrinopathy, monoclonal protein, and skin changes)
- e) Cohort C2: Subjects with active plasma cell leukemia (defined as either 20% of peripheral blood white blood cell count comprised of plasma/CD138+ cells or an absolute plasma cell count of $2 \times 10^9/L$)
- f) Current or history of clinically significant muscle disorders (e.g., myositis), recent unresolved muscle injury, or any condition known to elevate serum CK levels
- g) Subjects with an active, known or suspected autoimmune disease. Subjects with type I diabetes mellitus, hypothyroidism only requiring hormone replacement, skin disorders (such as vitiligo, psoriasis, or alopecia) not requiring systemic treatment, or conditions not expected to recur in the absence of an external trigger are permitted to enroll.
- h) Subjects with a condition requiring systemic treatment with either corticosteroids (> 10 mg daily prednisone equivalent) or other immunosuppressive medications within 14 days of treatment assignment Inhaled or topical steroids, and adrenal replacement steroid > 10 mg daily prednisone equivalent, are permitted in the absence of active autoimmune disease.
- i) Subjects with active or history of interstitial pneumonia or pulmonary fibrosis as diagnosed clinically or by imaging. Patients with radiation pneumonitis will be eligible if stabilization from fibrosis is confirmed and there is no concern for recurrence.
- j) Decreased cardiac function with NYHA $>$ Class 2
- k) Uncontrolled or significant heart disorder such as unstable angina
- l) Current unresolved infection or history of chronic, active, clinically significant infection (viral, bacterial, fungal, or other) which, in the opinion of the Investigator, would preclude the patient from exposure to a biologic agent or pose a risk to patient safety
- m) Known medical condition that, in the investigator's opinion, would increase the risk associated with study participation or study drug administration or interfere with the interpretation of safety results
- n) Evidence of coagulopathy or bleeding diathesis
- o) Any major surgery within 4 weeks of study drug administration
- p) Participants with a prior malignancy are excluded (except non-melanoma skin cancers, and in situ cancers such as the following: bladder, colorectal, cervical/dysplasia, melanoma, or breast). Participants with other second malignancies diagnosed more than 2 years ago who have received therapy with curative intent with no evidence of disease during the interval who are considered by the investigator to present a low risk for recurrence will be eligible.
- q) Other active malignancy requiring concurrent intervention

2) Prior/Concomitant Therapy

- a) Cohort M1 and M2 (cabiralizumab monotherapy), subjects with prior exposure to anti-CSF1R therapy
- b) Cohort C1 and C2 (cabiralizumab and Nivolumab combination therapy), subjects with prior exposure to both of anti-CSF1R therapy and anti-PD-1/PD-L1 antibody as either combination or sequential.
- c) Concomitant use of statins while on study. However, a patient using statins for over 3 months prior to study drug administration and in stable status without CK rise may be permitted to enroll
- d) Treatment with any anti-cancer therapy or participation in another investigational drug or biologics trial within 28 days prior to first dose of study drug administration
- e) Non-oncology vaccine therapies for prevention of infectious diseases (e.g., HPV vaccine) within 4 weeks of study drug administration. The inactivated seasonal influenza vaccine can be given to patients before treatment and while on therapy without restriction. Influenza vaccines containing live virus or other clinically indicated vaccinations for infectious diseases (i.e., pneumovax, varicella, etc.) may be permitted, but must be discussed with the Sponsor's Medical Monitor and may require a study drug washout period prior to and after administration of vaccine.
- f) Transfusion completed within 72 hours prior to first dose of study drug administration
- g) Cohort C2: Subject has undergone any allogeneic transplant
- h) Cohort C2: Subject has undergone autologous transplant within 100 days of initiation of study drugs.

3) Physical and Laboratory Test Findings

- a) Evidence of organ dysfunction or any clinically significant deviation from normal in physical examination, vital signs, ECG or clinical laboratory determinations beyond what is consistent with the target population
- b) Significant abnormalities on ECG at screening.
 - i) QTcF > 450 msec for males
 - ii) QTcF > 470 msec for females
- c) Positive blood screen for hepatitis C antibody, hepatitis B surface antigen, or HIV-1 and -2 antibody
- d) Positive test for latent tuberculosis (TB) at screening [Interferon-Gamma Release Assays (e.g. Quantiferon test)] or evidence of active TB

4) Allergies and Adverse Drug Reaction

- a) History of allergy to components of cabiralizumab and/or nivolumab.
- b) History of any significant drug allergy (such as anaphylaxis or hepatotoxicity)

5) Other Exclusion Criteria

- a) Prisoners or participants who are involuntarily incarcerated. (Note: under certain specific circumstances a person who has been imprisoned may be included or permitted to continue as a participant. Strict conditions apply and Bristol-Myers Squibb approval is required.
- b) Participants who are compulsorily detained for treatment of either a psychiatric or physical (e.g., infectious disease) illness

Eligibility criteria for this study have been carefully considered to ensure the safety of the study participants and that the results of the study can be used. It is imperative that participants fully meet all eligibility criteria.

6.3 Lifestyle Restrictions

Not applicable.

6.4 Screen Failures

Screen failures are defined as participants who consent to participate in the clinical study but are not subsequently assigned to treatment. A minimal set of screen failure information is required to ensure transparent reporting of screen failure participants, to meet the Consolidated Standards of Reporting Trials (CONSORT) publishing requirements, and to respond to queries from regulatory authorities. Minimal information includes date of consent, demography, screen failure details, eligibility criteria, and any serious AEs.

6.4.1 Retesting During Screening Period

Participant Re-enrollment: This study permits the re-enrollment of a participant that has discontinued the study as a pre-treatment failure (i.e., participant has not had treatment assignment). If re-enrolled, the participant must be re-consented

Retesting of laboratory parameters and/or other assessments within any single Screening period will be permitted (in addition to any parameters that require a confirmatory value).

The most current result prior to treatment assignment is the value by which study inclusion will be assessed, as it represents the participant's most current, clinical state.

7 TREATMENT

Study treatment is defined as any investigational treatment(s), marketed product(s), placebo or medical device intended to be administered to a study participant according to the study randomization or treatment allocation

Study treatment includes both Investigational [Medicinal] Product (IP/IMP) and Non-investigational [Medicinal] Product (Non-IP/Non-IMP) and can consist of the following:

- Cabiralizumab
- Nivolumab

An investigational product, also known as investigational medicinal product in some regions, is defined a pharmaceutical form of an active substance or placebo being tested or used as a reference in a clinical study, including products already with a marketing authorization but used or assembled (formulated or packaged) differently than the authorized form, or used for an unauthorized indication, or when used to gain further information about the authorized form.

Other medications used as support or escape medication for preventative, diagnostic, or therapeutic reasons, as components of the standard of care for a given diagnosis, may be considered as non-investigational products.

Table 7-1: Study treatments for CA025001

Product Description / Class and Dosage Form	Potency	IP/Non-IMP	Blinded or Open Label	Packaging / Appearance	Storage Conditions (per label)
Cabiralizumab (BMS-986227) Solution for Injection	100 mg/vial (20 mg/mL)	IP	Open Label	Vial	Refer to the label on container and/or pharmacy manual
Nivolumab Solution for Injection	100 mg/vial (10 mg/mL)	IP	Open Label	Vial	Refer to the label on container and/or pharmacy manual

7.1 Treatments Administered

The selection and timing of dose for each participant is as follows:

Table 7.1-1: Selection and Timing of Dose

Cohort	Study Treatment	Unit dose strength(s)/ Dosage level(s)	Dosage formulation Frequency of Administration	Route of Administration
M1 ^a	Cabiralizumab	2 mg/kg	Every 2 weeks	Intravenous
M2	Cabiralizumab	4 mg/kg	Every 2 weeks	Intravenous
C1/C2	Cabiralizumab	4 mg/kg	Every 2 weeks	Intravenous
	Nivolumab	3 mg/kg	Every 2 weeks	Intravenous

^a A lower dose may be tested if appropriate.

Sponsor has the option to expand combination cohorts (up to 12 subjects in total per each combination cohort) at the dose previously established to be safe in order to obtain additional data or to investigate alternative dose levels to those defined in the protocol.

No within-subject dose escalations will be permitted. If a dose level is found to exceed the MTD subjects enrolled in that dose level may be treated at a lower dose following consultation and agreement between Investigators, the Sponsor and Efficacy and Safety Review Committee.

7.2 Method of Treatment Assignment

All participants will be centrally assigned to treatment. Complete instructions will be provided in a separate manual.

Study treatment will be dispensed at the study visits as listed in Schedule of Activities (Section 2).

Enrolled participants, including those not dosed, will be assigned participant numbers comprised of the site number and subject number. For example, the first subject screened (ie, enrolled) at site number 1, will have a participant number of 0001 00101. Those enrolled participants meeting inclusion and exclusion criteria will be eligible to be dosed.

7.3 Blinding

Not applicable.

7.4 Dosage Modification

7.4.1 Dose Delay for Cabiralizumab and Nivolumab

Administration of cabiralizumab and/or nivolumab in combination therapy should be delayed for the following:

- Any Grade 3 fatigue which does not resolve to Grade 1 or baseline before the next treatment visit

- Any drug-related laboratory abnormalities would not require a dose delay unless clinically indicated or specified in the protocol or abnormal laboratory management table ([Appendix 8](#)). Please discuss with the Sponsor's Medical Monitor or designee as needed.
- For dose delays or modifications for all other AEs please refer to the AE management tables in [Appendix 6](#) and [Appendix 7](#).

Patients who require a dose delay of cabiralizumab or cabiralizumab/nivolumab should be re-evaluated weekly or more frequently if clinically indicated and resume study drug dosing when re-treatment criteria are met. If a patient experiences an infusion reaction to cabiralizumab, or nivolumab, or both study drugs, the infusion reaction should be treated following the infusion reaction treatment guidelines in [Section 7.4.5](#), Appendix 6, and Appendix 7. If the causality of the AE requiring a dose delay is confirmed to be due to one of the study drugs of the combination therapy, the non-offending drug may be continued per protocol taking into account the safety and clinical benefit to the patient.

7.4.2 Criteria to Resume Treatment with Cabiralizumab and Nivolumab

Patients may resume treatment with cabiralizumab and/or nivolumab when the drug-related AE resolves as noted in the AE management tables in Appendix 6 and Appendix 7 or the abnormal laboratory management table in Appendix 8. The Sponsor's Medical Monitor or designee can be contacted at any time if further clarification is needed.

7.4.3 Dose Reduction with Cabiralizumab and Nivolumab

Dose reduction for cabiralizumab and Nivolumab are not permitted.

7.4.4 Treatment beyond Disease Progression with Cabiralizumab and Nivolumab in Subjects with Solid Tumor

Accumulating evidence indicates a minority of patients treated with immunotherapy may derive clinical benefit despite initial evidence of progressive disease.

Patients treated with cabiralizumab and nivolumab combination therapy will be permitted to continue cabiralizumab and nivolumab treatment beyond initial RECIST v1.1 defined progressive disease, assessed by the Investigator, as long as the following criteria are met:

- Patients who will be treated beyond disease progression must review and sign an ICF before continuing on study drug
- The patient demonstrates investigator-assessed clinical benefit, and do not have rapid disease progression
- Tolerance of study drugs
- Stable performance status
- Treatment beyond progression will not delay an imminent intervention to prevent serious complications of disease progression (e.g., CNS metastases)

A radiographic assessment/scan should be performed approximately 8 weeks (± 7 days) after initial Investigator-assessed progression to determine whether there has been a decrease in the tumor size

or continued progressive disease. The assessment of clinical benefit should be balanced by clinical judgment as to whether the patient is clinically deteriorating and unlikely to receive any benefit from continued treatment with cabiralizumab and nivolumab.

If the Investigator feels that any patient receiving cabiralizumab and nivolumab will obtain clinical benefit by continuing treatment, the patient may remain on the trial and continue to receive monitoring according to the time and event schedules per protocol.

For the patients who continue cabiralizumab and nivolumab study therapy beyond progression, further progression is defined as an additional 10% increase in tumor burden from time of initial progression. This includes an increase in the sum of diameters of all target lesions and/or the diameters of new measurable lesions compared to the time of initial progression. cabiralizumab and nivolumab treatment should be discontinued permanently upon documentation of further progression.

7.4.5 *Treatment of Cabiralizumab and Nivolumab-Related Infusion Reactions*

Cabiralizumab and nivolumab may induce infusion or hypersensitivity reactions. If such reactions were to occur, it may manifest with fever, chills, rigors, headache, rash, pruritus, arthralgia, hypo- or hypertension, bronchospasm, or other symptoms.

Infusion reactions should be graded according to CTCAE v4 guidelines. Any Grade 3 or Grade 4 infusion reaction should be reported within 24 hours to the Sponsor's Medical Monitor or designee, and reported as an SAE if it meets the criteria.

The nivolumab 30-minute infusion will be administered first, with a 30-minute rest, followed by the cabiralizumab 30-minute infusion. It may be unclear if an infusion reaction is due to cabiralizumab, nivolumab, or to both study drugs. Therefore, one set of treatment recommendations (based on the most conservative treatments for infusion reactions due to either study drug) is provided below and may be modified based on clinical judgment, local treatment standards and guidelines, and/or specific symptoms, as appropriate:

For Grade 1 symptoms: Mild reaction (e.g., localized cutaneous reactions including mild pruritus, flushing, rash), requires infusion rate to be decreased; intervention may be indicated.

- Decrease the rate of the study drug infusion until recovery from symptoms.
- Remain at bedside and monitor the patient's vital signs until resolution of symptoms. Diphenhydramine 50 mg may be administered at the discretion of the treating physician.
- When symptoms resolve, restart the infusion at the original infusion rate.
- If a patient has an infusion reaction with nivolumab, cabiralizumab can be given (without prophylactic medications) if the infusion reaction resolves within 3 hours. For scheduling purposes, cabiralizumab infusion may be given the next day. Prophylactic pre-infusion medications should be given prior to all subsequent nivolumab infusions.
- If a patient has an infusion reaction with cabiralizumab, prophylactic pre-infusion medications should be given prior to all subsequent cabiralizumab and nivolumab infusions.
- The following prophylactic pre-infusion medications are recommended prior to future infusions of cabiralizumab and nivolumab: diphenhydramine 50 mg (or equivalent) and/or

paracetamol (acetaminophen) 325 to 1000 mg at least 30 minutes before additional study drug administrations.

For Grade 2 symptoms: Moderate reaction (i.e., any symptom not listed above [mild symptoms] or below [severe symptoms] such as generalized pruritus, flushing, rash, dyspnea, hypotension with systolic blood pressure >80 mmHg), requires infusion interruption but responds promptly to symptomatic treatment (e.g., antihistamines, nonsteroidal anti-inflammatory drugs, narcotics, corticosteroids, IV fluids); prophylactic pre-infusion medications indicated for ≤ 24 hours.

- Interrupt the study drug infusion.
- Begin an IV infusion of normal saline, and treat the patient with diphenhydramine 50 mg IV (or equivalent) and/or paracetamol (acetaminophen) 325 to 1000 mg.
- Remain at bedside and monitor the patient's vital signs until resolution of symptoms. Corticosteroid therapy may be administered at the discretion of the treating physician.
- When symptoms resolve, restart the infusion at 50% of the original infusion rate; if no further complications ensue after 30 minutes, the rate may be increased to 100% of the original infusion rate.
- Monitor the patient closely. If symptoms recur, immediately discontinue the infusion; no further study drug will be administered at that visit. Administer diphenhydramine 50 mg IV, and remain at bedside and monitor the patient until resolution of symptoms.
- If a patient has an infusion reaction with nivolumab infusion, cabiralizumab infusion can be given (without prophylactic medications) if the infusion reaction resolves within 3 hours. For scheduling purposes, the cabiralizumab infusion may be given the next day. Prophylactic pre-infusion medications should be given prior to all subsequent nivolumab infusions.
- If a patient has an infusion reaction with cabiralizumab, prophylactic pre-infusion medications should be given prior to all subsequent cabiralizumab and nivolumab infusions.
- The following prophylactic pre-infusion medications are recommended prior to future infusions of cabiralizumab and nivolumab: diphenhydramine 50 mg (or equivalent) and/or paracetamol (acetaminophen) 325 to 1000 mg should be administered at least 30 minutes before additional study drug administrations. If necessary, corticosteroids (up to 25 mg of SoluCortef or equivalent) may be used.
- The amount of study drug infused must be recorded.

For Grade 3 or Grade 4 symptoms: Severe reaction such as bronchospasm, generalized urticaria, systolic blood pressure <80 mmHg, or angioedema; Grade 3 symptoms including prolonged symptoms, which require 6 or more hours to respond to symptomatic medication and/or discontinuation of infusion; recurrence of symptoms following initial improvement; hospitalization indicated for other clinical sequelae, such as renal impairment, pulmonary infiltrates; Grade 4: life-threatening; pressor or ventilation support indicated.

- Immediately discontinue the study drug infusion. No further study drug will be administered. The amount of study drug infused must be recorded on the CRF.
- Begin an IV infusion of normal saline, and treat the patient as follows: Recommend bronchodilators, epinephrine 0.2 to 1.0 mg of a 1:1,000 solution for subcutaneous administration or 0.1 to 0.25 mg of a 1:10,000 solution injected slowly for IV administration,

and/or diphenhydramine 50 mg IV with methylprednisolone 100 mg IV (or equivalent), as needed.

- Remain at bedside and monitor the patient's vital signs until recovery from symptoms.
- The patient should be monitored until the Investigator is comfortable that the symptoms will not recur.
- Investigators should follow their institutional guidelines for the treatment of anaphylaxis.

In the case of late-occurring hypersensitivity symptoms (e.g., appearance of a localized or generalized pruritus within 1 week after treatment), symptomatic treatment may be given (e.g., oral antihistamine, or corticosteroids).

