Grade 2	– Delay cabiralizumab therapy per protocol	If returns to Grade 1 or baseline before the next dosing visit: – Resume cabiralizumab therapy at same dose level without delay – Routine eye monitoring per protocol, if clinically stable If swelling persists >14 days but returns back to baseline or Grade 1 within 28 days: – Continue cabiralizumab therapy upon resolution – If it recurs at Grade 2 or above, discontinue cabiralizumab therapy
Grade ≥3	– Discontinue cabiralizumab therapy per protocol.	If returns to Grade 1 after discontinuation: – Follow up until resolution

Infusion Reactions Adverse Event Management		
Grade of Infusion Reactions (NCI CTCAE v 4.03)	Management	Follow-Up
Grade 1	
 - Decrease infusion rate of cabiralizumab therapy per protocol and restart at normal infusion rate once symptoms subside. - Monitor patient and start symptomatic treatment as clinically indicated which includes antihistamines and NSAIDs 	
If infusion reaction symptoms subside within 3 hours of cabiralizumab therapy:
 
 - Subsequent dosing should include prophylactic pre-infusion medications for cabiralizumab therapy - Continue cabiralizumab dosing at same level
Grade 2	
 - Interrupt cabiralizumab infusion - Systemic treatment including NSAIDs, corticosteroids, and antihistamines - Normal saline infusion and constant monitoring of vitals and other parameters - If symptoms resolve, resume infusion at 50% of the infusion rate and then increase to 100% if clinically stable 	
 - Resume cabiralizumab therapy at same dose level - Future dosing with pre-infusion prophylactic medications recommended including antihistamines, NSAIDs, and corticosteroids up to 25 mg as needed 
If symptoms recur:
 
 - Discontinue treatment at the visit

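### Protocol Section 7.4.5 treats an infusion reaction that recurs on restart as Grade 2 with a stop for that visit, and also lists recurrence as Grade 3 with no further drug, so worst grade and the discontinuation count can differ for the same event.

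*Protocol*

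**What the plan says.** In Section 7.4.5 of the protocol, a Grade 2 reaction leads to interruption, symptomatic treatment and, once symptoms resolve, a restart at half the infusion rate. For a reaction that returns, the instruction is "If symptoms recur, immediately discontinue the infusion; no further study drug will be administered at that visit". The same list looks ahead to later doses: after a reaction to cabiralizumab, "prophylactic pre-infusion medications should be given prior to all subsequent cabiralizumab and nivolumab infusions". The Grade 2 infusion-reaction rows of Appendix 6 (monotherapy) and Appendix 7 (combination) carry the same visit-level stop: "Discontinue treatment at the visit".

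The Grade 3 or Grade 4 paragraph of 7.4.5 names several severe features. One is "recurrence of symptoms following initial improvement"; another is "prolonged symptoms, which require 6 or more hours to respond to symptomatic medication". Its action is "No further study drug will be administered", with no limit to the visit. Section 8.1.1 discontinues treatment for Grade 3 or higher infusion reactions and requires consultation with the medical monitor before any re-initiation. The Grade 3 or higher rows of Appendices 6 and 7 also discontinue therapy.

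Section 5.1.1.1 counts drug-related non-hematologic events of Grade 3 or higher in the first 28 days as DLTs. It excludes a Grade 3 infusion-related event that resolves within 6 hours of onset, but counts any recurrence of a Grade 3 infusion-related event.

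**The concern.** Take a moderate reaction that is interrupted, settles, and returns when the infusion is restarted. Both paragraphs of 7.4.5 describe it. One keeps it at Grade 2 and expects the participant back for the next dose. The other makes it Grade 3 and ends study drug. Nothing says which paragraph governs.

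Three recorded items then depend on the paragraph a site follows:

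- **Worst grade.** Protocol Section 10.3.2 and SAP Sections 7.6.2 to 7.6.4 tabulate AEs by worst CTC grade.
- **Expedited reporting.** Section 7.4.5 requires Grade 3 or 4 infusion reactions to reach the medical monitor within 24 hours; Grade 2 reactions carry no such duty.
- **AEs leading to discontinuation.** This is a named component of the primary endpoint for the monotherapy cohorts and of the secondary safety endpoint for the combination cohorts. SAP Section 7.1.1 takes it from the action recorded for study drug, so the two paragraphs produce different entries.

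**Working it through.** The plan states no figure for this point and no rate of reactions that recur on restart. The check is a comparison of texts, followed by a case analysis for DLT status.

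**Step 1. The two treatments of one event**

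| Item | Grade 2 paragraph of 7.4.5; Grade 2 rows of Appendices 6 and 7 | Grade 3/4 paragraph of 7.4.5; Section 8.1.1; Grade 3 or higher rows |
|---|---|---|
| Role of recurrence | An event to be managed within Grade 2 | A feature that defines Grade 3 |
| Drug at that visit | Stopped | Stopped |
| Later doses | Foreseen, with pre-medication (7.4.5) | None, unless re-initiated after consultation |
| 24-hour report to the medical monitor | Not required by grade | Required |
| Counted as AE leading to discontinuation | No | Yes |

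Only the handling at that visit agrees.

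**Step 2. When DLT status depends on the paragraph**

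Inputs: the 6-hour exclusion and the recurrence clause in Section 5.1.1.1, and the separate 6-hour response criterion in the Grade 3 paragraph of 7.4.5. Assume that the event is drug-related and falls within the 28 days.

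- **(a) The whole reaction resolves within 6 hours of first onset.** If Grade 2, it is not a DLT. If Grade 3, it is excluded as transient. It is not a DLT either way.
- **(b) Symptoms need 6 hours or more to respond.** The reaction is Grade 3 on duration, whatever is said about recurrence, and is not transient. It is a DLT either way.
- **(c) Each episode responds in under 6 hours, but the whole reaction is not resolved within 6 hours of first onset.** If Grade 2, it is not a DLT. If Grade 3, it is a DLT when the clock starts at first onset. If the clock restarts at the recurrence and that episode resolves within 6 hours, it is excluded. Section 5.1.1.1 does not say which onset is meant.
- **(d) The first reaction is labelled Grade 3, treatment is re-initiated after consultation, and the reaction recurs at a later dose.** On the 14-day schedule the second dose falls on Day 1 + 14 = Day 15, inside the 28 days. With the Grade 3 label, the recurrence clause makes this a DLT, and that clause does not repeat the 6-hour exclusion. If both reactions are kept at Grade 2, there is no DLT.

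DLT status therefore turns on the paragraph only in (c) and (d). A return within one infusion does not literally meet the recurrence clause if the first episode was Grade 2, but Section 5.1.1.1 does not settle this.

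**Step 3. When discontinuation depends on the paragraph**

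It differs in (a) and (c): dosing continues with pre-medication under one paragraph and stops under the other. In (b) both routes reach Grade 3. In (d) the first reaction already carries the difference. The conflict over discontinuation is thus wider than the conflict over DLTs.

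**The case against.** The strongest reply is that the documents already name a grading standard. Section 7.4.5 says that infusion reactions are graded by CTCAE v4, and it defines Grade 2 as a residual class that excludes whatever is listed as severe. On that reading, recurrence leaves Grade 2 as soon as it happens. But the recurrence instruction in 7.4.5 and those in the two Grade 2 appendix rows would then have almost no application. The reference to CTCAE also does not tell a site which of the two printed consequences to follow.

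A second reply is that the Grade 3 wording means relapse without re-exposure, whereas the Grade 2 wording concerns symptoms that return on restart. That would make the texts consistent, but the Grade 3 paragraph states no such limit.

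A third reply is that the SAP rule is clear, because discontinuations come from the CRF action field. That is correct. The problem lies upstream, in what sites do and record.

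Three stronger inferences should be resisted. A reader might infer that DLT status generally depends on the paragraph used. The 6-hour exclusion and the 6-hour response criterion remove most of that, and Section 5.1.1.1 sends such events to the investigator, sponsor/medical monitor and committee for determination. A reader might also take the Grade 3 route as permanent in every case, but Section 8.1.1 allows re-initiation after consultation, and 7.4.5 lets its recommendations be modified by clinical judgment. Finally, one event is 1/3 = 33 percentage points of a 3-subject cohort or 1/6 = 17 points of a 6-subject cohort, and one more DLT can change a cell of Table 5.1.1-1, for example from E at 0 of 3 to S at 1 of 3. Those statements hold for any single event in a cohort this small and do not measure this conflict.

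**Conclusion.** The inconsistency is real and should be corrected. A reaction that recurs after restart has two grades and two treatment consequences in the protocol, and the appendices repeat the split. Its firm effects are on worst grade, 24-hour reporting and AEs leading to discontinuation. Its effect on DLT status is confined to cases (c) and (d) and remains subject to adjudication. DLT counts drive only the monotherapy escalation.

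The size is at most one participant's grade and discontinuation entry per affected event. How many events would be affected is unknown, so no effect on the mTPI decisions is quantified. The conclusion assumes that the Grade 3 wording on recurrence includes recurrence on restart, which is its plain reading.

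**What to change.** Reconcile the Grade 2 and Grade 3/4 paragraphs of Section 7.4.5, the infusion-reaction rule in Section 8.1.1, and the infusion-reaction rows of Appendices 6 and 7, so that recurrence after restart has one grade and one consequence. In Section 5.1.1.1, state from which onset the 6 hours run and whether a recurrence within the same infusion counts as a recurrence. The sponsor decides the rule; this review takes no position on which is clinically right.

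The cost is protocol wording in three sections and two appendices. The SAP's rule for counting discontinuations can stay as it is.
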